13.5 Efficacy Analyses

Efficacy analysis will be conducted on the FAS and PPS. The interpretation of results from statistical tests will be based on the FAS. The PPS will be used to assess the robustness of the results from the statistical tests based on the FAS.

Efficacy within certain subgroups of clinical interest (e.g., age, sex, race, and ethnicity) will be examined. Further details on the subgroups of interest will be specified in the SAP.

Change from baseline in average AM rTNSS and iTNSS over the first 6, 30, and 52 weeks of treatment will be analyzed using an analysis of covariance (ANCOVA) model adjusting for study treatment group, site, and baseline (defined as the average of the last 4 consecutive AM assessments during the last 4 days of the run-in period from the Day -3 AM assessment to the AM assessment on the day of randomization). At least 2 out of 4 assessments (scores) should be available in order to calculate the baseline scores for the AM rTNSS and iTNSS (linear, continuous covariate). Least squares means (LSMs) of the treatment differences and associated 95% confidence intervals (95% CIs) and p-values will be presented. A multiple, imputation-based approach where complete data sets are drawn will be used for handling missing data in the efficacy analysis. The imputation model will be defined and fully detailed in the SAP.

Changes from baseline in rTNSS and iTNSS at the end of each week of treatment and changes from baseline in individual nasal symptom scores over the first 6, 30, and 52 weeks (and at the end of each treatment week) of the treatment period will be analyzed in a similar manner as described above.

Changes from baseline in RQLQ(S) at Weeks 6, 30, and 52 will be analyzed for the FAS and the RQLQ(S) Analysis Set using ANCOVA models adjusting for study treatment group, site, and baseline RQLQ(S) (linear, continuous covariate). For subjects who withdraw early from the study, the RQLQ(S) score at their discontinuation visit will be used.

The analyses of RCAT results will be similar to the RQLQ(S) analyses except the RQLQ(S) analysis set will not apply.

Detailed statistical analyses and methods will be provided in the SAP.

13.6 Pharmacokinetic, Pharmacodynamic, Biomarker, and Pharmacogenomic/Pharmacogenetic Analyses

Not applicable.

13.7 Safety Analyses

Unless otherwise specified, 'baseline' will be defined as the last available assessment prior to the first dose of study medication following randomization.

13.7.1 Extent of Exposure

The number of subjects exposed to each study treatment will be summarized. The number of days on treatment and the number of days on study (run-in plus treatment periods) will be summarized by study treatment. In addition, treatment compliance will be summarized by categories (details will be provided in the SAP) and study treatment.

13.7.2 Adverse Events

Adverse events will be coded using the current Medical Dictionary for Regulatory Activities (MedDRA). Adverse events occurring between the signing of informed consent and administration of the first dose of randomized study medication will be regarded as pre-treatment AEs and included in the subject listings but not in the summary tables. Adverse events occurring after the first dose of randomized study medication will be defined as TEAEs.

The safety endpoints related to AEs are:

- Proportion of subjects with TEAEs.
- Proportion of subjects with treatment-related TEAEs.
- Incidence, type, and severity of the TEAEs after 30 weeks of study treatment.
- Incidence, type, and severity of the TEAEs after 52 weeks of study treatment.

The number and percentage of subjects with TEAEs will be summarized by study treatment group, overall, and by system organ class (SOC) and preferred term (PT) using frequency counts and percentages. The summaries will also include the number of TEAEs experienced. A similar summary will be produced for subjects with treatment-related TEAE.

The number and percentage of subjects with a TEAE that has a start date within 30 weeks of the start of treatment (≤ 182 days) will be summarized by severity and study treatment group, overall, and by SOC and PT using frequency counts and percentages. A similar summary will be produced including all TEAEs during the study (i.e., after 52 weeks of treatment).

If sufficient data exist, TEAE frequencies will be compared across treatment groups using Fisher's exact test or a similar test.

Additionally, the number and percentage of SAEs, TEAEs leading to discontinuation, and TEAEs related to the IP will be summarized by SOC, PT, and study treatment group. All AEs will be displayed in listings. AEs that occur during the run-in period will be summarized separately.

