11.8 Treatment Visit: Visit 8 (Week 30 ±7 Days)

The following procedures and evaluations will be performed at this visit:

1. Distribution of RQLQ(S), review instructions with the subject, and subject completion of RQLQ(S). This must be the first procedure performed.

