13.1 Sample Size

The sample size of 600 subjects for this study (400 subjects on GSP 301 NS and 100 subjects in each of the 2 placebo groups) is based on the ICH E1 Guideline (ICH E1)¹⁹ and the FDA Guidance on Allergic Rhinitis,¹⁴ which requires treatment of at least 300 subjects for 6 months and 100 subjects for 1 year. Based on an estimated attrition rate of 25% after 6 months and 50% after 52 weeks, 400 subjects in the GSP 301 NS treatment group are considered sufficient to meet the above requirements.

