### 4.0 Study Endpoints

#### 4.1 Primary Endpoints

- Proportion of subjects with treatment-emergent adverse events (TEAEs).
- Proportion of subjects with treatment-related TEAEs.
- Incidence, type, and severity of the TEAEs after 30 weeks of study treatment.
- Incidence, type, and severity of the TEAEs after 52 weeks of study treatment.
- Clinical laboratory assessments (hematology, serum biochemistry, and urinalysis) at baseline, Week 30, and Week 52.
- Vital signs, physical examinations (PE), and focused ears, nose, and throat (ENT) and eye examinations at baseline, Week 30, and Week 52.

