### 12.2.2 Adverse Events

All AEs will be coded according to the current version of MedDRA (version 18.1 or later). Adverse events occurring between the subjects signing informed consent and administration of the first dose of the randomized study medication will be regarded as pre-treatment AEs and will be included in the subject listings but not in the summary tables. Adverse events occurring after the first dose of the randomized study medication will be defined as treatment-emergent adverse events (TEAEs) and will be listed and summarized by System Organ Class (SOC) and Preferred Term (PT).

The safety endpoints related to AEs are:

- Proportion of subjects with TEAEs.
- Proportion of subjects with treatment-related TEAEs.
- Incidence, type, and severity of the TEAEs after 30 weeks of study treatment.
- Incidence, type, and severity of the TEAEs after 52 weeks of study treatment.

Summaries of the number and percentage of subjects with TEAEs and the number of TEAEs experienced will be presented by treatment group. The number of subjects and the number of TEAEs will be presented using frequency counts and percentages, overall and by SOC and PT. The percentages will be calculated as the number of subjects with TEAEs divided by the number of subjects in the safety analysis set. Tables of the number and percentage of subjects and the number of TEAEs by intensity and by relationship to study medication will also be presented. Similar tables will be created for treatment related AEs. Events will be assigned to the study treatment administered prior to the start of the TEAE. Events that occurred during discharge and final follow-up will be assigned to the final treatment.

The number and percentage of subjects with a TEAE that has a start date within 30 weeks of the start of treatment ( $\leq 182$  days) will be summarized by severity and study treatment group, overall, and by SOC and PT using frequency counts and percentages. A similar summary will be produced including all TEAEs during the study (i.e., after 52 weeks of treatment).

The overall p-value of the comparison among three treatment groups by SOC and PT will be produced using Fisher's exact test for each SOC and PT as well as overall subjects with at least one TEAEs. .

|  |                                    |                                  |
|--|------------------------------------|----------------------------------|

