| Moderate (n2(%))                                | xxx (xx.x)                                     | xxx (xx.x)                                     | xxx (xx.x)               |
| Severe (n2(%))                                  | xxx (xx.x)                                     | xxx (xx.x)                                     | xxx (xx.x)               |
| Not Related (n2(%))                             | xxx (xx.x)                                     | xxx (xx.x)                                     | xxx (xx.x)               |
| Related (n2(%))                                 | xxx (xx.x)                                     | xxx (xx.x)                                     | xxx (xx.x)               |
| Death (n2(%))                                   | xxx (xx.x)                                     | xxx (xx.x)                                     | xxx (xx.x)               |
| Serious AE (n2(%))                              | xxx (xx.x)                                     | xxx (xx.x)                                     | xxx (xx.x)               |

N1: number of subjects in safety analysis sets in treatment group; n1(%): percentage based on N1

N2: number of adverse events in treatment group; n2(%): percentage based on N2

Data source: xx

Created on: ddmmmyy hh:mm

Page 1 of N

**T14.1.9.5.2 Overall Summary of Treatment Emergent Adverse Events after 30 Weeks of Study Treatment  
(Safety Analysis Set)**

Repeat of T14.1.9.5.1 for after 30 weeks of study treatment

|  |                                    |                                  |
|--|------------------------------------|----------------------------------|
| Protocol Number:
GPL/CT/2014/018/III
(Study No. GSP 301-303) | SAP Version Number:
Version 1.0 | SAP Version Date:
04-Apr-2017 |
|--|------------------------------------|----------------------------------|

**T14.1.9.5.3 Summary of Treatment Emergent Adverse Events after 52 Weeks of Study Treatment  
(Safety Analysis Set)**

| Body System                    | MedDRA Term | GSP 301 placebo
NS pH [REDACTED]
(N=xxx) |                  | GSP 301 placebo
NS pH [REDACTED]
(N=xxx) |                  | GSP 301
NS
(N=xxx) |                  | Fisher's
P-value |
|--------------------------------|-------------|--|------------------|--|------------------|--------------------------|------------------|---------------------|

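### The 30-week TEAE summary, a primary endpoint, is cut at 182 days, which is 26 weeks; 30 weeks is 210 days.

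*Protocol*

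**What the plan says.** SAP 4.1 lists among the primary endpoints "Incidence, type, and severity of the TEAEs after 30 weeks of study treatment"; the protocol synopsis lists the same endpoint.

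The operational rule is in Protocol 13.7.2: the summary counts subjects with a TEAE that "has a start date within 30 weeks of the start of treatment (≤ 182 days". SAP 12.2.2 repeats the words, "has a start date within 30 weeks of the start of treatment", and follows them with the same 182-day limit. The companion summary has no day limit: "A similar summary will be produced including all TEAEs during the study (i.e., after 52 weeks of treatment".

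Elsewhere Week 30 means Visit 8. Its protocol heading is "11.8 Treatment Visit: Visit 8 (Week 30 ±7 Days", and the schedule in Protocol Appendix 1 and SAP Appendix 2 places it at Day 211 ± 7.

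Seven SAP tables carry a 30-week title: T14.1.9.5.2, .4, .6, .10, .13, .16 and .18. Their shells give no day rule. The shell for T14.1.9.5.2, for example, says only "Repeat of T14.1.9.5.1 for after 30 weeks of study treatment".

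Protocol section 13 says the SAP prevails where the two differ. Here they agree. SAP 1.0, which lists changes from the protocol, does not mention the cut-off.

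**The concern.** The sentence contradicts itself: the words say 30 weeks and the bracketed number says 26. The number is the only day limit either document gives for a 30-week adverse event table, so it is what a programmer is likely to code.

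Three things are at stake.

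- The output concerns a primary endpoint of a trial whose primary objective is long-term safety. Counted to Day 182, incidence is too low for the title in every arm, as are the counts in each severity grade.
- T14.1.9.5.4 and T14.1.9.5.6 repeat the layout of T14.1.9.5.3, which has a Fisher's exact p-value column. The cut therefore affects p-values as well as counts.
- The Week 30 laboratory, vital sign and physical examination data come from Visit 8. An adverse event window closing at Day 182 ends weeks before those assessments, so results presented together as Week 30 would cover different periods.

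**Working it through.** **Inputs from the documents**

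- Stated limit: ≤ 182 days, equated with 30 weeks (Protocol 13.7.2; SAP 12.2.2).
- Week 30 visit: Day 211 ± 7 (Protocol Appendix 1; SAP Appendix 2).
- Planned GSP 301 arm: 400 subjects, with attrition of 25% at 6 months (Protocol 13.1; SAP 8.0).

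**Step 1. Can 182 be reproduced as 30 weeks?**

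- 30 × 7 = 210.
- Scheduled Week 30 day: 30 × 7 + 1 = 211.
- Earliest day in the Week 30 window: 211 − 7 = 204.
- 26 × 7 = 182, and half a year is 365 / 2 = 182.5.

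Only 26 weeks or half a year gives the stated figure.

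**Step 2. Do the documents count weeks in some other way?** All ten post-randomization visits satisfy day = 7 × week + 1: 22, 43, 85, 127, 169, 211, 253, 295, 337, 365. The SAP compliance formula also uses seven-day weeks (2 × 7 × 52 = 728). Counting elapsed days instead of study days moves a boundary by one day, not 28.

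**Step 3. Size of the gap (no assumptions needed)**

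- 210 − 182 = 28 days, or 4 weeks; 28 / 210 = 13.3% of the window.
- Visit 8 window: Days 204 to 218. Gap from the cut to the visit: 204 − 182 = 22 to 218 − 182 = 36 days.

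**Step 4. Share of subject-time lost on GSP 301.** Assume a constant dropout hazard that matches the planned attrition, taking 6 months as 182 days.

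- d = −ln(0.75) / 182 = 0.001581 per day.
- Subject-days to day t = 400 × (1 − e^(−dt)) / d.
- To Day 182: 63,264. From Day 182 to Day 210: 8,217. Total: 71,481.
- 8,217 / 71,481 = 11.5%.

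**Step 5. Illustration of the effect on the reported percentage.** The documents give no TEAE rates, so one-year risks of 30%, 50% and 70% are assumed, each with a constant hazard l = −ln(1 − risk) / 364. Subjects who drop out stop contributing events but stay in the denominator: F(t) = l / (l + d) × (1 − e^(−(l + d)t)).

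| Assumed 1-year risk | F at Day 182 | F at Day 210 | Difference (points) | Share of first TEAEs missed |
|---|---|---|---|---|
| 30% | 14.3% | 15.9% | 1.7 | 10.4% |
| 50% | 25.7% | 28.4% | 2.7 | 9.5% |
| 70% | 39.9% | 43.4% | 3.6 | 8.2% |

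Differences are taken before rounding. A simpler version without dropout, with 52-week risks of 20% to 60%, gives 10.6% to 36.8% at Day 182 against 12.1% to 41.1% at Day 210, a gap of 1.5 to 4.3 points.

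**The case against.** The arithmetic cannot be defended, but several points limit its consequence.

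- **The loss is conditional.** It occurs only if the bracketed number is coded rather than the words. That is correct. But the number is the only programmable rule given, and leaving the choice to the programmer is itself a defect.
- **No safety data leave the study.** Events on Days 183 to 210 remain in the 52-week tables, in the special-interest tables (which have no 30-week cut) and in the listings. The overall TEAE proportion, the treatment-related proportion and the 52-week endpoint are unaffected. This stands.
- **The rule is attached to one display.** Both sections state it for the summary by severity (T14.1.9.5.10); extending it to the other six tables is inference. It is a fair reading, since the SAP gives no other definition of the 30-week window.
- **Alignment with Visit 8 is imperfect under any fixed cut.** ENT and eye examinations occur at every visit, and Day 210 falls inside the Day 204 to 218 window, so some findings first recorded at Visit 8 could still fall after it. That is true, but a cut inside the visit window is much closer than one 22 to 36 days before the visit.
- **No biased comparison or shift in the severity mix is shown.** The same cut applies to all arms, and SAP 6.0 states no formal hypotheses. This stands: the fault is lower counts under a wrong label.
- **26 weeks may have been intended**, perhaps from the exposure guideline, "which requires treatment of at least 300 subjects for 6 months and 100 subjects for 1 year". The documents do not say so. If it was, the endpoint wording and seven table titles are wrong instead.

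**Conclusion.** The cut-off is wrong as written. Both documents equate 30 weeks with 182 days, while the endpoint wording, the table titles and the visit schedule all point to 210.

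The certain part is the 28-day shortfall, 13.3% of the window. The 11.5% loss of subject-time rests on the planned attrition and a constant dropout hazard. The understatement of 1.7 to 3.6 points, equal to 8% to 10% of subjects with a first TEAE by Week 30, also assumes a constant event hazard and one-year risks of 30% to 70%. If first events cluster early, it is smaller.

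The error matters because it sits in the definition of a primary endpoint. Choosing between 182 and 210 after unblinding would be a post-hoc decision.

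**What to change.** In Protocol 13.7.2 and SAP 12.2.2, replace ≤ 182 days with ≤ 210 days and state the day count, for example with the first randomized dose as Day 1, so that 30 weeks is Days 1 to 210. Record the correction in SAP 1.0.

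State that this window applies to all the 30-week TEAE, treatment-related TEAE and SAE tables (T14.1.9.5.2, .4, .6, .10, .13, .16 and .18), and put the limit in their footnotes.

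If a six-month cut is also wanted for the exposure guideline, add it as a separate table titled 26 weeks.

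The cost is one number and a short definition in the text and programming specification. No new data are needed. It should be done before database lock.

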13.7.3 Laboratory Data

The laboratory data (hematology, biochemistry, and urinalysis), will be summarized for each visit at which laboratory assessments are done (Screening Visit [Visit 1], Week 30 [Visit 8], and Week 52 [Visit 12]). In addition, values outside the normal range and values deemed as

clinically significant by the Investigator will be listed. The data will be summarized using descriptive statistics. All laboratory data will be displayed in listings.

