## STATISTICAL ANALYSIS PLAN

|  |                                    |                                  |
|--|------------------------------------|----------------------------------|
| Protocol Number:
GPL/CT/2014/018/III
(Study No. GSP 301-303) | SAP Version Number:
Version 1.0 | SAP Version Date:
04-Apr-2017 |
|--|------------------------------------|----------------------------------|

Descriptive statistics (number of subjects, mean, standard deviation, median, minimum and maximum) will be presented for laboratory data as well as change from baseline by treatment and visit.

Baseline is defined as the last available lab values at Screening Visit [Visit 1].

In addition, values outside the normal range and values deemed as clinically significant by the Investigator will be listed. The number of subjects with values of potentially clinical significance determined by the investigator will be tabulated by treatment group and visit.

Shift tables will present changes from baseline in laboratory data (categorized as normal; abnormal, not clinically significant; and abnormal, clinically significant) to end of treatment.

All laboratory data will be listed by treatment and subject.

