| Protocol Number:
GPL/CT/2014/018/III
(Study No. GSP 301-303) | SAP Version Number:
Version 1.0 | SAP Version Date:
04-Apr-2017 |
|--|------------------------------------|----------------------------------|

**T14.1.9.6.4 Summary of Potentially Clinical Significant Laboratory Results (Biochemistry)  
(Safety Analysis Set)  
Lab Test: xxxxx**

| Treatment Group                          | Visit    | Normal
n(%) | Abnormal
n(%) | Abnormal (NCS)
n(%) | Abnormal(CS)
n(%) |
|--|----------|----------------|------------------|------------------------|----------------------|
| GSP 301 placebo NS pH [redacted] (N=xxx) | Baseline | xxx (xx.x)     | xxx (xx.x)       | xxx (xx.x)             | xxx (xx.x)           |
|  | Visit 8  | xxx (xx.x)     | xxx (xx.x)       | xxx (xx.x)             | xxx (xx.x)           |
|  | Visit 12 | xxx (xx.x)     | xxx (xx.x)       | xxx (xx.x)             | xxx (xx.x)           |

GSP 301 placebo NS pH [redacted] (N=xxx)  
GSP 301 NS (N=xxx)

Baseline is defined as the last available lab values at Screening Visit [Visit 1].  
CS= Clinically Significant, NCS= Not Clinically Significant

Table will continue for other lab tests.

Data source: xx  
Created on: ddmmmyy hh:mm Page 1 of N

|  |                                    |                                  |
|--|------------------------------------|----------------------------------|
| Protocol Number:
GPL/CT/2014/018/III
(Study No. GSP 301-303) | SAP Version Number:
Version 1.0 | SAP Version Date:
04-Apr-2017 |
|--|------------------------------------|----------------------------------|

**T14.1.9.6.5 Summary of Potentially Clinical Significant Laboratory Results (Hematology)  
(Safety Analysis Set)**

Repeat of T14.1.9.6.4 for hematology

**T14.1.9.6.6 Summary of Potentially Clinical Significant Laboratory Results (Urinalysis)  
(Safety Analysis Set)**

Repeat of T14.1.9.6.4 for urinalysis

|  |                                    |                                  |
|--|------------------------------------|----------------------------------|
| Protocol Number:
GPL/CT/2014/018/III
(Study No. GSP 301-303) | SAP Version Number:
Version 1.0 | SAP Version Date:
04-Apr-2017 |
|--|------------------------------------|----------------------------------|

**T14.1.9.6.7 Shift Tables for Changes from Baseline in Laboratory Results (Biochemistry) to End of Treatment  
(Safety Analysis Set)**

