|  |                | Lab Test: xxxxx |                   |                            |                           |
|--|----------------|------------------------|-------------------|----------------------------|---------------------------|
| Treatment Group                          | Baseline       | End of Treatment       |                   |                            |                           |
|  |                | Normal
n (%)        | Abnormal
n (%) | Abnormal
(NCS)
n (%) | Abnormal
(CS)
n (%) |
| GSP 301 placebo NS pH [redacted] (N=xxx) | Normal         | xxx (xx.x)             | xxx (xx.x)        | xxx (xx.x)                 | xxx (xx.x)                |
|  | Abnormal       | xxx (xx.x)             | xxx (xx.x)        | xxx (xx.x)                 | xxx (xx.x)                |
|  | Abnormal (NCS) | xxx (xx.x)             | xxx (xx.x)        | xxx (xx.x)                 | xxx (xx.x)                |
|  | Abnormal (CS)  | xxx (xx.x)             | xxx (xx.x)        | xxx (xx.x)                 | xxx (xx.x)                |

GSP 301 placebo NS pH [redacted] (N=xxx)  
GSP 301 NS (N=xxx)

Baseline is defined as the last available lab values at Screening Visit [Visit 1].  
CS= Clinically Significant, NCS= Not Clinically Significant

Table will continue for other lab tests.

Data source: xx

Created on: ddmmyy hh:mm

Page 1 of N

|  |                                    |                                  |
|--|------------------------------------|----------------------------------|
| Protocol Number:
GPL/CT/2014/018/III
(Study No. GSP 301-303) | SAP Version Number:
Version 1.0 | SAP Version Date:
04-Apr-2017 |
|--|------------------------------------|----------------------------------|

**T14.1.9.6.8 Shift Tables for Changes from Baseline in Laboratory Results (Hematology) to End of Treatment (Safety Analysis Set)**

Repeat of T14.1.9.6.7 for hematology

**T14.1.9.6.9 Shift Tables for Changes from Baseline in Laboratory Results (Urinalysis) to End of Treatment (Safety Analysis Set)**

Repeat of T14.1.9.6.7 for urinalysis

|  |                                    |                                  |
|--|------------------------------------|----------------------------------|
| Protocol Number:
GPL/CT/2014/018/III
(Study No. GSP 301-303) | SAP Version Number:
Version 1.0 | SAP Version Date:
04-Apr-2017 |
|--|------------------------------------|----------------------------------|

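### The SAP's laboratory abnormality and shift tables count high and low values together, which dilutes a one-directional effect and hides its direction in those tables

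*Protocol*

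**What the plan says.** SAP 4.1 names as a primary endpoint: "Clinical laboratory assessments (hematology, serum biochemistry, and urinalysis) at baseline, Week 30, and Week 52".

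Protocol 13.7.3 calls for descriptive statistics by visit and a listing of abnormal values, introduced by "In addition, values outside the normal range and values deemed as" clinically significant. It plans no laboratory shift or abnormality table, so the tables at issue come from the SAP.

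SAP 12.2.4 has three relevant elements:
- Signed numeric summaries: descriptive statistics "will be presented for laboratory data as well as change from baseline by treatment and visit". The shells are T14.1.9.6.1 to 6.3.
- Counts by arm and visit of subjects whose values the investigator judges potentially clinically significant. Shell T14.1.9.6.4 has the columns "Normal n(%) | Abnormal n(%) | Abnormal (NCS) n(%) | Abnormal(CS) n", and 6.5 repeats it for hematology.
- Shift tables showing "changes from baseline in laboratory data (categorized as normal; abnormal, not clinically significant; and abnormal, clinically significant) to end of treatment". Shell T14.1.9.6.7 ("Shift Tables for Changes from Baseline in Laboratory Results (Biochemistry) to End of Treatment") crosses "Baseline | End of Treatment" in the same non-directional categories, and 6.8 repeats it for hematology.

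A High flag next to a normal range appears only in the subject-level biochemistry listing, L16.2.8.1.

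**The concern.** Most of the chemistry and hematology tests in Protocol Appendix 3 are numeric and can be out of range at either end: glucose, potassium, leukocytes, eosinophils and platelets, for example. In the planned counts, a value that goes high and a value that goes low fall in the same column. A drug that pushes a test one way adds subjects at one end of the range and removes some at the other. The combined count records only the net change, against a background that includes both tails. A subject who goes from high to low, with the same clinical-significance call at both times, sits in an abnormal-to-abnormal cell and reads as no shift.

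The protocol itself gives a reason to look at direction: its introduction (5.1) says that intranasal corticosteroids reduce eosinophilia. The planned counts could not say which way eosinophils moved in any arm.

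**Working it through.** **Plan figures.** The documents give no laboratory distributions or abnormality rates, so there is no laboratory figure to reproduce. The one sample-size figure does reproduce: 300 / (1 − 0.25) = 400 on GSP 301 NS, and 400 × 0.50 = 200, above the 100 required at one year. Each placebo arm has 100.

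**Step 1: is there a directional count by arm?** T14.1.9.6.1 to 6.3 give the mean, SD, median, minimum and maximum of observed values and of change. That is signed, but it is not a count. T14.1.9.6.4 to 6.9 give counts, but without direction. L16.2.8.1 gives direction, but one subject at a time. No planned table counts subjects by arm as high or low.

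**Step 2: how much is diluted?** Assume one test with normally distributed values, a reference range that leaves 2.5% in each tail, and a uniform upward shift of d SD.

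- High = 1 − Φ(1.96 − d)
- Low = Φ(−1.96 − d)
- Share offset = (2.5% − Low) / (High − 2.5%)

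| d (SD) | High | Low | Combined | Share offset |
|---|---|---|---|---|
| 0 | 2.5% | 2.5% | 5.0% | n/a |
| 0.2 | 3.9% | 1.5% | 5.5% | 68% |
| 0.3 | 4.9% | 1.2% | 6.0% | 56% |
| 0.5 | 7.2% | 0.7% | 7.9% | 38% |
| 1.0 | 16.9% | 0.2% | 17.0% | 16% |

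For d = 0.5 the share is (2.5 − 0.69) / (7.21 − 2.5) = 1.81 / 4.71 = 38%. It falls below one half at d of about 0.36.

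**Step 3: sensitivity to the assumed tails, at 0.5 SD.**

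| Tails | Share offset |
|---|---|
| 1% each | 32% |
| 5% each | 45% |
| 1% low, 2.5% high | 16% |
| 5% low, 2.5% high | 72% |

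Among subjects normal at baseline (the main row of the shift table), with a baseline-to-end correlation of 0.5 to 0.85 and 2.5% tails, the share is 58–66% at 0.2 SD, 27–36% at 0.5 SD and 9–15% at 1.0 SD.

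**Step 4: illustrative detection, 400 vs 100, two-sided 5%, d = 0.5.** No laboratory test is planned, so this only shows lost resolution.

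| Method | High only | Combined |
|---|---|---|
| Fisher's exact | 38% | 12% |
| Normal approximation, pooled variance | 38% | 14% |
| Normal approximation, unpooled variance | 64% | 21% |

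The last row should not be relied on: only 2.5 high values are expected among 100 placebo subjects, too few for that approximation. A comparison of mean change under the same model (SD of change 1, assumed) has about 99% power at 0.5 SD and 77% at 0.3 SD.

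**The case against.** The strongest reply is that direction is not lost from the analysis. T14.1.9.6.1 to 6.3 give signed change by arm and visit, and for a uniform shift that summary is far more sensitive than any count of abnormal values (Step 4). Minimum and maximum show the extremes. Clinically significant abnormalities are recorded as adverse events under Protocol 12.4, apart from those associated with the underlying disease and no more severe than expected. Flags and ranges are listed by subject. The same normal/NCS/CS scheme serves vital signs and ECGs, so it is a consistent choice built around the investigator's judgement. SAP Appendix 1 also says that its shells are a framework that may be modified.

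Much of this stands, and it lowers the priority. It also limits what can be claimed. A reader might infer that a one-directional effect largely cancels. With equal 2.5% tails that is true only for shifts below about 0.36 SD; at 0.5 SD about 62% of the rise survives and at 1.0 SD about 84%. For a test that is abnormal in one direction only, nothing cancels. If only a few subjects respond, the opposite tail hardly falls, so there is little offset in that case either.

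What the reply does not supply is a by-arm count of subjects leaving the range at each end. A mean can barely move when a minority of subjects change, and the extremes describe one subject per arm. The framework caveat does not help either, because the categories are fixed in the text of SAP 12.2.4 as well as in the shells.

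**Conclusion.** The point holds as a limitation of the SAP's abnormality and shift tables, not as a failure of the laboratory analysis as a whole. Those tables combine high and low values, so they dilute a one-directional effect, hide its direction, and can show a high-to-low or low-to-high move as no change. That last point needs no distributional assumption.

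The size of the dilution does need assumptions: normal values, a uniform shift and an assumed share in each tail. On those terms the offset is moderate at 0.5 SD (38%, with a range of 16% to 72% over the tails tried) and small at 1.0 SD. It exceeds one half only for small shifts or where the opposite tail starts out heavier. Power figures are illustrative only. The defect lies in the SAP; listing abnormal values, as Protocol 13.7.3 does, is not an error.

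**What to change.** In SAP 12.2.4 and shells T14.1.9.6.4, 6.5, 6.7 and 6.8:
- Classify each numeric chemistry and hematology value as Low, Normal or High against the central-laboratory range.
- Give by-arm counts in those categories at Week 30 and Week 52, and the shift from baseline to end of treatment in the same categories.
- Keep the investigator's CS/NCS call as a separate column.
- Leave urinalysis as normal/abnormal.

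The cost is a paragraph of SAP text and four shells, with somewhat wider tables. No new data are needed, since results are already held against normal ranges for the listings. Make the change before database lock and unblinding, so that direction is not first examined post hoc.
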